The use of lasers to selectively target chromophores in the skin was first described by Anderson and Parrish in 1983¹ which led directly to the development of the first pulsed dye laser to be used in dermatology to treat vascular lesions. As laser technology advanced shorter pulse duration lasers, such as nanosecond pulse duration domain Q-switched Ruby and Nd:YAG lasers among others, were developed to safely and effectively remove tattoos and pigmented lesions using the same principles of selective photothermolysis.³⁻⁵ Further advances led to the introduction of lasers with pulse durations in the picosecond domain including the Nd:YAG at wavelengths of 532 nm, 1064 nm; and the alexandrite at 755 nm which have both been demonstrated as safe and effective for treatment of benign pigmented lesions, wrinkles, tattoo removal, and other indications.⁶⁻¹³

5. Study Design

This is a prospective, non-randomized, multi-center, evaluator blinded, safety and efficacy clinical study. Subjects will serve as their own control as the appearance of their benign pigmented lesions and/or wrinkles at baseline is compared to the appearance following laser treatment.

6. Study Overview

Subjects will participate in a Screening Visit to evaluate the presence of benign pigmented lesions including dyschromia, or wrinkles including fine lines. After evaluating all inclusion and exclusion criteria, and providing signed informed consent, subjects will be considered enrolled in the study and assigned a unique identification number that will appear on all records for that subject as the Subject ID.

Subjects will then either be scheduled for the Baseline / Treatment Visit #1 at a later date, or the Screening and Baseline / Treatment #1 Visits may be combined into the same visit.

Subjects will receive up to four (4) study laser treatments at 6 ± 2 week treatment intervals.

NOTE: Fewer than four (4) Treatment Visits may be required to reach maximum expected clinical results in some subjects. Treatments may therefore be stopped, and subject placed into the Follow-Up phase at the discretion of the Investigator.

The Study Doctor or staff will make up to three (3) attempts to contact subjects by telephone 10 days after each treatment to assess healing response.

After the final study laser treatment, subjects will be scheduled for three (3) follow-up visits at 4 ± 2 week intervals, or approximately 1, 2 and 3 months.

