Local skin responses will be assessed and recorded following each laser treatment, normally within the first 30 minutes. The Local Skin Response Form is provided in Appendix E and includes the following most commonly observed skin responses which are both anticipated and in some instances desired clinical endpoints:

- Erythema
- Edema
- Whitening
- Petechiae
- Pinpoint Bleeding
- Purpura
- Crusting
- Blistering
- Burning

Safety Assessment

Local skin responses occurring from prior laser treatments that are deemed more serious due will be recorded as Adverse Device Effects (ADE) on the appropriate study case report form. Examples of anticipated ADE that can be observed following treatment with the PicoWay™ laser include:

- Hyperpigmentation
- Hypopigmentation
- Scarring
- Infection
- Herpes Simplex Activation

Although highly uncommon in conjunction with PicoWay® laser treatments, any Unanticipated Adverse Device Effects (UADE) will also be recorded on case report forms and reported to the Sponsor and IRB as required.

Post-Treatment Care Instruction

Subjects will receive instructions on post-treatment care of their treated areas. These may include the application of a petrolatum gel (such as Aquaphor® or Vaseline®); use of a topical corticosteroid (such as Cortizone®); avoiding sun exposure or use of tanning equipment; and use of a sunscreen with sun protection factor (SPF) 30 or greater for the duration of study.

Telephone Contacts

The Study Doctor or staff will make up to three (3) attempts to contact subjects by telephone 10 days after each treatment (+/- 7 Days) to assess healing response.

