10.3. Follow-Up Visits

Subjects will be scheduled for follow-up visits at 4 ± 1 weeks, 8 ± 2 weeks, and 12 ± 2 weeks after their final study treatment visit, or approximately 1, 2 and 3 months. Additional visits may be scheduled by the Investigator as needed.

Photography

Treatment areas will be photographed at all follow-up visits using the same camera settings used previously at Baseline and Treatment Visits.

Subject Satisfaction

Subjects will be asked to rate their level of satisfaction with the study treatments thus far at each follow-up visit using the Subject Satisfaction Scale provided in Appendix C.

Skin Biopsy (optional)

Subjects who have provided prior written consent may have one or more skin biopsy taken from the treated area at the discretion of the Investigator. Biopsy procedure details are provided in the Treatment Visit section above.

11. Schedule of Events

The Study Schedule of Events is provided in Table 1.

NOTE: The Screening and Baseline / Treatment #1 Visits may be combined in the same visit.

NOTE: Fewer than four (4) Treatment Visits may be required to reach maximum expected clinical results in some subjects. Treatments may therefore be stopped, and subject placed into the Follow-Up phase at the discretion of the Investigator.

Table 1: Study Visits and Schedule of Events

Activity	Screening	Baseline Tx 1	Tx 2	Tx 3	Tx 4	1 Month Follow- Up	2 Month Follow- Up	3 Month Follow- Up
	0 to -2 Weeks	Day 0	Week 6 ± 2 Weeks	Week 12 ± 2 Weeks	Week 18 ± 2 Weeks	Week 22 ± 2 Weeks	Week 26 ± 2 Weeks	Week 30 ± 4 Weeks
Informed Consent	X							
Medical History/Concomitant Medications	X							
Inclusion/Exclusion Criteria	X							
Treatment Site ID	X							
Pregnancy Test	X	X	X	X	X			
Skin Biopsy (Optional)		X	X	X	X	X	X	X
Telephone Contact*		X	X	X	X			
Photography		X	X	X	X	X	X	X
Laser Treatment		X	X	X	X			
Subject Pain Score		X	X	X	X			
Subject Satisfaction			X	X	X	X	X	X
Safety Assessment (LSR, ADE, UADE)		X	X	X	X	X	X	X
Concomitant Medications	X	X	X	X	X	X	X	X
Study Exit								X

*10 Days post-treatment (+/- 7 Days)

12. Study Compliance

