19.5. Safety Analyses

Safety will be evaluated using the Local Skin Response (Appendix E) which will specifically assess the following nine pre-defined safety endpoints: erythema, edema, whitening, petechiae, pinpoint bleeding, purpura, crusting, blistering, burn, as well as other to be graded on a 5-point ordinal score.

Safety will be evaluated in the Intent to Treat (ITT) population which includes all treated subjects. Safety results will be displayed separately for Groups A and Group B. Analyses will include a summary of the incidence, severity, and relatedness of all reported local skin responses, adverse device effects, and unanticipated adverse device effects. In addition, the percentage with no adverse device effects will also be reported as well as the percentage according to worst overall degree; a similar evaluation will be performed for the worst degree for those at least related to the study treatment. The percent reporting each ordinal score per safety endpoint will be presented separately for each stratum and combined.

20. Histological Analysis

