21.1. Potential Risks

The study treatments to be administered in this trial carry risks of local skin responses that are common, expected, and at times even desired with study treatments. The skin responses are typically only trace to moderate, and transient in nature, resolving within a few days after treatment.

Common local skin responses or side effects of treatment include erythema, edema, whitening, petechiae, pinpoint bleeding, purpura, crusting, blistering, and burning following the treatment.

Examples of less common but potentially more severe or lingering local skin responses associated with PicoWay™ laser treatment include hyperpigmentation, hypopigmentation, herpes virus activation, infection and scarring.

Allergic reactions to the topical or injectable anesthesia products are also possible.

There is also a risk of eye injury associated with the use of any laser device. This risk is very uncommon as it is easily prevented if proper safety eyewear is used as required.

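### No graded local skin response assessment is scheduled between about 30 minutes after treatment and the next clinic visit, so the section 19.5 grade tables can miss responses that develop and clear in between

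*Combined protocol and SAP*

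**What the plan says.** **Timing of the grade.** Section 10.2 sets the post-treatment assessment: "Local skin responses will be assessed and recorded following each laser treatment, normally within the first 30 minutes". The form is Appendix E, which offers None, Trace, Mild, Moderate and Severe for each response and defines none of these grades.

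**Expected course.** Section 21.1: "The skin responses are typically only trace to moderate, and transient in nature, resolving within a few days after treatment".

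**Next clinic visit.** Section 6: "Subjects will receive up to four (4) study laser treatments at 6 ± 2 week treatment intervals". For the period after the last treatment, section 10.3 has: "Subjects will be scheduled for follow-up visits at 4 ± 1 weeks, 8 ± 2 weeks, and 12 ± 2 weeks after their final study treatment visit". Section 6 has: "subjects will be scheduled for three (3) follow-up visits at 4 ± 2 week intervals". Table 1 places the first follow-up at Week 22 ± 2 weeks, with treatment 4 at Week 18.

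**Order within a visit.** The synopsis visit outline for Treatment Visits 2 to 4 lists the laser treatment before the local skin response assessment.

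**Contact between visits.** A telephone call follows each treatment (section 10.2, with up to three attempts). The Table 1 footnote times it at "10 Days post-treatment (+/- 7 Days"). Its stated purpose is to assess healing. No form, grade or question list is named.

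**Carry-over.** Section 10.2, Safety Assessment: "Local skin responses occurring from prior laser treatments that are deemed more serious due will be recorded as Adverse Device Effects (ADE". Sections 22.1 and 22.2 define an ADE more widely, as any device-related adverse event whether expected or not. They collect ADEs from consent to study exit, with onset date, severity and outcome, and follow them to resolution.

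**Endpoint and analysis.** Section 17.2 puts the incidence, severity and relatedness of local skin responses in the primary safety endpoint; the synopsis version names adverse device effects only. Section 19.5 names nine responses as pre-defined safety endpoints and adds: "The percent reporting each ordinal score per safety endpoint will be presented separately for each stratum and combined".

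**The concern.** The plan promises incidence and severity for nine responses, among them crusting, blistering, purpura and burn. For each treatment, the one graded look scheduled within their stated course is at about half an hour. A response that starts or worsens later and is gone by the next visit has no scheduled graded record, unless someone reports it and it is entered as an ADE.

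The section 19.5 tables would then describe immediate responses while reading as the incidence and severity of each response. Section 14 classes the 730 nm and Resolve Fusion handpieces as investigational, so these tables are part of the safety description that the trial is meant to supply.

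**Working it through.** The plan states no figure on this point, so there is nothing to reproduce. The check converts the visit windows to days and sets them against the stated course.

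**Inputs.** Immediate look at 30 minutes (10.2). Treatment interval 6 ± 2 weeks (6). First follow-up at 4 ± 1 weeks (10.3) or 4 ± 2 weeks (6). Call at day 10 ± 7 (10.2, Table 1). The course is given only as a few days (21.1); I assume 2 to 7 days.

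**Step 1: next scheduled clinic assessment.**
- Between treatments: (6 − 2) × 7 = 28 to (6 + 2) × 7 = 56 days.
- After the last treatment, section 10.3: (4 − 1) × 7 = 21 to (4 + 1) × 7 = 35 days.
- After the last treatment, section 6: (4 − 2) × 7 = 14 to (4 + 2) × 7 = 42 days. Table 1 agrees if treatment 4 is at its nominal Week 18: (20 − 18) × 7 = 14 to (24 − 18) × 7 = 42 days.

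Every window opens after a 7-day course has ended. The smallest margin is 14 − 7 = 7 days.

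**Step 2: where the 30-minute look falls.** Thirty minutes as a share of a course of d days is 0.5 / (24 × d): 1.0% for d = 2, 0.7% for d = 3 and 0.3% for d = 7.

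**Step 3: where the call falls.** The window runs from day 10 − 7 = 3 to day 10 + 7 = 17, which is 15 days. Window days inside a course of d days are max(0, d − 3 + 1): 0 of 15 for d = 2, 1 of 15 for d = 3 and 5 of 15 for d = 7. At nominal day 10 the call comes after all of these courses have ended.

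**Step 4: what the form grades at Treatment Visits 2 to 4.** The outline places the form after the laser treatment, and section 10.2 ties it to the treatment just given. As listed, it grades the new treatment. A subject with four treatments then has one scheduled grade, at about 30 minutes, for each of treatments 1 to 3. Only the last treatment is followed by visits at which the form is completed without new laser exposure.

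**Step 5: trace one case.** Take, for illustration only, a blister that appears on day 1 and clears by day 5.
- 30-minute form: not yet present.
- Call on day 10: can be mentioned, but no grade is called for.
- Next visit, day 14 at the earliest: resolved.
- ADE record under section 10.2: only if deemed more serious, with no criterion given.
- ADE record under section 22.1: qualifies if it is an adverse event related to the device.

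Whether the blister reaches the database depends on which section the site follows. Even if entered as an ADE, nothing says that it feeds the grade distribution by response in section 19.5.

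**Step 6: severity.** Table 4, written for ADEs and UADEs, uses the same None-to-Severe labels as Appendix E and defines them partly by duration (24 hours, 7 days, more than 2 weeks, more than 6 months). If Table 4 also governs Appendix E, a look at 30 minutes cannot observe that duration. If it does not, the Appendix E grades are undefined.

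**The case against.** The strongest reply is that the interval is not unobserved. ADEs are collected continuously, with onset date, severity and outcome, and are followed to resolution. The definition includes expected effects, and Table 4 has grades for reactions lasting under 24 hours or up to 7 days. A call follows every treatment, and extra visits are allowed. Section 19.5 also summarises all reported ADEs and UADEs, and the form is completed again at each follow-up visit.

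Much of this stands. A reader might infer that late responses are graded nowhere, that the safety endpoint misses most of their course, or that the trial cannot meet its safety objective. The documents do not support those readings. The ADE route exists; section 17.2 asks for incidence, severity and relatedness rather than duration; the synopsis endpoint rests on ADEs alone; and longer-lasting effects such as scarring or pigment change would still be captured. Nor does the call's separate row in Table 1 show what it records: the columns are visits, so a call can only be a row, and the case report forms are not in the documents.

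It does not close the gap. Section 10.2 narrows the ADE route to more serious carry-over responses, in conflict with section 22.1. Extra visits are discretionary and cannot support an incidence estimate. The call has no stated grade and no place in the analysis.

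A second objection concerns the remedy. At day 10 most responses will have cleared, and subjects must recall and grade signs such as petechiae or whitening. That is correct, and it is a reason to keep telephone grades apart from site grades.

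**Conclusion.** The point holds in a limited form. No graded local skin response assessment is scheduled between about 30 minutes and the next clinic visit. That visit is at day 28 to 56 between treatments, and after the last treatment at day 21 to 35 or day 14 to 42, depending on the section. With a course of 2 to 7 days (my assumption for a few days), all these windows open at least 7 days after resolution. The section 19.5 grade tables can therefore miss responses that appear or worsen after the first half hour and clear before the next visit.

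The possible error is understatement, but its size cannot be derived: the documents give no onset or peak time for any of the nine responses. They equally give no basis for treating 30 minutes as the peak. The conclusion concerns the local skin response tables and does not extend to the ADE and UADE part of the safety endpoint.

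**What to change.** 1. **Section 10.2 and Table 1.** Have the existing telephone contact record, for each of the nine Appendix E responses, whether it occurred since treatment, the worst subject-reported grade, and the days of onset and resolution.
2. **Section 19.5.** Label the 30-minute results as immediate responses. Tabulate the telephone-reported responses separately, per treatment. Any worst grade combining the two sources should be supplementary.
3. **Reconcile the conflicting passages.** Sections 10.2 and 22.1 differ on when a local skin response is an ADE. The synopsis and section 17.2 differ on whether these responses belong to the primary safety endpoint. Section 10.3 differs from section 6 and Table 1 on the first follow-up window.

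The cost is one case report form page per call (at most four per subject) and a few sentences of text. It adds no visit. The telephone grades will be recalled and subject-reported, usually after resolution, and the reported rates will probably be somewhat higher.

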10.3. Follow-Up Visits

Subjects will be scheduled for follow-up visits at 4 ± 1 weeks, 8 ± 2 weeks, and 12 ± 2 weeks after their final study treatment visit, or approximately 1, 2 and 3 months. Additional visits may be scheduled by the Investigator as needed.

Photography

Treatment areas will be photographed at all follow-up visits using the same camera settings used previously at Baseline and Treatment Visits.

Subject Satisfaction

Subjects will be asked to rate their level of satisfaction with the study treatments thus far at each follow-up visit using the Subject Satisfaction Scale provided in Appendix C.

Skin Biopsy (optional)

Subjects who have provided prior written consent may have one or more skin biopsy taken from the treated area at the discretion of the Investigator. Biopsy procedure details are provided in the Treatment Visit section above.

11. Schedule of Events

The Study Schedule of Events is provided in Table 1.

NOTE: The Screening and Baseline / Treatment #1 Visits may be combined in the same visit.

NOTE: Fewer than four (4) Treatment Visits may be required to reach maximum expected clinical results in some subjects. Treatments may therefore be stopped, and subject placed into the Follow-Up phase at the discretion of the Investigator.

Table 1: Study Visits and Schedule of Events

Activity	Screening	Baseline Tx 1	Tx 2	Tx 3	Tx 4	1 Month Follow- Up	2 Month Follow- Up	3 Month Follow- Up
	0 to -2 Weeks	Day 0	Week 6 ± 2 Weeks	Week 12 ± 2 Weeks	Week 18 ± 2 Weeks	Week 22 ± 2 Weeks	Week 26 ± 2 Weeks	Week 30 ± 4 Weeks
Informed Consent	X							
Medical History/Concomitant Medications	X							
Inclusion/Exclusion Criteria	X							
Treatment Site ID	X							
Pregnancy Test	X	X	X	X	X			
Skin Biopsy (Optional)		X	X	X	X	X	X	X
Telephone Contact*		X	X	X	X			
Photography		X	X	X	X	X	X	X
Laser Treatment		X	X	X	X			
Subject Pain Score		X	X	X	X			
Subject Satisfaction			X	X	X	X	X	X
Safety Assessment (LSR, ADE, UADE)		X	X	X	X	X	X	X
Concomitant Medications	X	X	X	X	X	X	X	X
Study Exit								X

*10 Days post-treatment (+/- 7 Days)

12. Study Compliance

This study will be conducted in compliance with this Protocol, guidelines as provided by the device manufacturer, Candela Corporation, in the PicoWay® User Manuals and Treatment Guides, Sponsor Standard Operating Procedures (SOP), and other applicable guidance as provided by 21CFR 812, ICH GCP EC(R2), or other local regulatory authorities. Confidentiality and privacy of subjects' medical information will be maintained in compliance with the Health Insurance Portability and Accountability Act (HIPAA).

13. Study Device

13.1. PicoWay® Laser System

The PicoWay® laser system is an alexandrite laser pumped, solid-state Neodymium:Yttrium Aluminum Garnet (Nd:YAG) laser emitting energy at user selectable wavelengths of 1064 nm, 532 nm, 785 nm or 730 nm [REDACTED]
[REDACTED]
[REDACTED]

At the 1064 nm and 532 nm wavelengths the ZOOM handpiece is provided that allows the spot size of the beam delivered to the treatment area to be adjusted from a [REDACTED]
[REDACTED] in increments of [REDACTED]

At the 785 nm and 730 nm wavelengths Titanium:Sapphire full surface handpieces are provided with selectable distance gauges that allow selection of [REDACTED]
[REDACTED] spot sizes.

At the 1064 nm and 532 nm wavelengths, a Resolve™ fractional handpiece is provided which transforms the laser beam [REDACTED]
[REDACTED]

At the 1064 nm and 532 nm wavelengths, a Resolve™ Fusion fractional handpiece is provided which transforms the laser beam into a fractional 10 X 10 array of 101 individual microbeams equally spaced within a 6 mm X 6 mm square spot size. Each microbeam produced by the Resolve™ Fusion handpiece consists of a central beam of energy surrounded by an annular “ring beam”.

Safety Eyewear is provided with each laser system and must be worn by all personnel in the treatment room while the laser is being used, including the patient.

13.2. Technical Specifications

Technical specifications for the PicoWay® Laser System are provided in Table 2.

Table 2: Laser System Technical Specifications				
PicoWay™ Laser System				
Parameter	Specifications			
Wavelength	█	█	█	█
Pulse Duration (nominal)	█	█	█	█
Maximum Radiant Energy	█	█	█	█
Pulse Repetition Rate	█	█	█	█
Fluence (max) ZOOM handpiece	█	█	█	█
Fluence (max) Ti:Sapphire handpiece	█	█	█	█
Energy (max) Resolve™ handpiece	█	█	█	█
Energy (max) Fusion central beam	█	█	█	█
Fluence (max) Fusion ring beam				
Safety Eyewear (minimum)	█	█	█	█
Spot Size	█ █ █ █			
Delivery System	█ █ █ █			
Aiming Beam	█ █ █ █			

[redacted due to confidential information]

13.3. Device Training

Qualified, designated study personnel at each investigational site will receive device specific training from the Sponsor on the PicoWay® laser system prior to performing study laser treatments.

14. Regulatory Approvals

The base system of the PicoWay® Laser System and handpieces at the 1064 nm, 785 nm and 532 nm wavelengths have received multiple 510(k) market clearances by the U.S. Food and Drug Administration (FDA) as shown in Table 3. Specific cleared indications for use are also listed below.

The 730 nm and Resolve™ Fusion handpieces planned for use in this study are at this time considered Investigational Devices by the Food and Drug Administration and will therefore be labeled with the following statement:

“CAUTION - Investigational Device. Limited by Federal (or United States) law to investigational use.”

Table 3: FDA 510(k) Premarket Notifications for Candela PicoWay® Laser System

510(k) Number	Device Name
[REDACTED]	PicoWay Laser

14.1. Indications for Use

The PicoWay® Laser System is indicated for the following at the specified wavelength:

532nm: Removal of tattoos for Fitzpatrick skin types I-III to treat the following colors: red, yellow and orange.

785nm: Removal of tattoos for Fitzpatrick skin types II-IV to treat the following tattoo colors: green and blue.

1064nm: Removal of tattoos for all skin types (Fitzpatrick I-VI) to treat the following tattoo colors: black, brown, green, blue, and purple.

The PicoWay® Laser System is also indicated for benign pigmented lesions removal for Fitzpatrick Skin Types I-IV.

The Resolve™ handpiece (1064nm) is also indicated for the treatment of acne scars in Fitzpatrick Skin Types II-V.

The Resolve™ handpieces are also indicated for treatment of wrinkles in Fitzpatrick Skin Types I-IV.

15. Non-Significant Risk Determination

In accordance with the definition of “Significant Risk Device” provided in the U.S. Code of Federal Regulation 21 CFR 812.3, each device to be used in the study has been determined to be a Non-Significant Risk (NSR) device based on the following:

- a) It is not an implant
- b) It is not purported or represented to be for use in supporting or sustaining human life and do not present a potential for serious risk to the health, safety or welfare of a subject
- c) It is not for a use of substantial importance in diagnosing, curing, mitigating, or treating disease or otherwise preventing impairment of human health
- d) Use of the device poses no risk to the health, safety, or welfare of a subject

16. Institutional Review Board (IRB)/Independent Ethics Committee (IEC)

This study will begin enrollment of subjects only after receiving written approval from the appropriate Institutional Review Board (IRB), Independent Ethics Committee (IEC) or other regulatory authorities deemed necessary depending on specific country or local requirements. Any sites selected outside of the United States will need to meet the country requirements for conducting human research studies.

17. Study Endpoints

